#### APPENDIX 14.3: WISH TREATMENT GUIDELINES BY ETIOLOGIC OR SYNDROMIC DIAGNOSIS

Diagnosis	Treatment (follow latest Rwandan guidelines)	Other Follow-Up
Gonorrhea Positive GeneXpert NG test. Treat regardless of the presence of symptoms.	1 st choice: Ciprofloxacin 1g single oral dose 2 nd choice: Ceftriaxone 250 mg in one single IM dose	
 
In female sex workers, also consider the possibility of rectal or pharyngeal NG (take throat and rectal swabs for testing if suspected).
 
Actively follow-up participants with laboratory-confirmed NG approximately 7 days after treatment to check for treatment failure (due to NG resistance). If symptoms are still reported, give the 2nd choice treatment.
 
Male partners should be treated in the same manner as the female index case. Couples should be treated around the same time and counseled to abstain from sex or use condoms during treatment to avoid re-infections.
 

Chlamydia Positive GeneXpert CT test.	1 st choice: Doxycyclin 100 mg twice per day for 7 days 2 nd choice: Erythromycin 1g twice per day for 7 days	
 
Most CT infections are asymptomatic so active follow-up after treatment is not useful.
 
Male partners should be treated in the same manner as the female index
 

Treat regardless of the presence of symptoms.		case. Couples should be treated around the same time and counseled to abstain from sex or use condoms during treatment to avoid re-infections.
Trichomoniasis Positive TV OSOM test. Treat regardless of the presence of symptoms.	
 
1st choice: Metronidazole 2 g single oral dose
 
OR Metronidazole 400 or 500 mg orally twice per day for 7 days
 
2nd choice: Tinidazole 2g single oral dose OR Tinidazole 500 mg twice per day for 7 days
 
	
 
If BV is also present (see below), the 7 day treatment is preferred because it is more effective against BV. However, if poor adherence is suspected, use a single dose treatment.
 
Male partners should also be treated in the same manner as the female index case. Couples should be treated around the same time and counseled to abstain from sex or use condoms during treatment to avoid re-infections.
 

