Treatments (or prescriptions) given by a study physician	MV ¹	AV ^{1,2,3}	Total ^{1,4}
	n (%)	n (%)	n (%)
	N = 705	N = xxx	N = 705
- None			
- Metronidazole 7 days po for BV and/or TV			l
- Metronidazole single dose po for BV and/or TV ⁵			l
- Fluconazole single dose po for vaginal candidiasis			1
- Clotrimazole vaginal pessaries 3 nights for vaginal candidiasis			
- Clotrimazole vaginal pessaries 3 nights for vaginal candidiasis			
 Clotrimazole vaginal pessaries 3 nights for vaginal candidiasis Antibiotic for UTI, PID, CT, NG, syphilis or genital ulcers / inguinal 			
 Clotrimazole vaginal pessaries 3 nights for vaginal candidiasis Antibiotic for UTI, PID, CT, NG, syphilis or genital ulcers / inguinal buboes [categories to be specified] 			
 Clotrimazole vaginal pessaries 3 nights for vaginal candidiasis Antibiotic for UTI, PID, CT, NG, syphilis or genital ulcers / inguinal buboes [categories to be specified] Antibiotic for another reason: [categories to be specified] 			
 Clotrimazole vaginal pessaries 3 nights for vaginal candidiasis Antibiotic for UTI, PID, CT, NG, syphilis or genital ulcers / inguinal buboes [categories to be specified] Antibiotic for another reason: [categories to be specified] Acyclovir 5-7 days po for genital ulcers/herpes 			

Abbreviations: AV = additional visit; BV = bacterial vaginosis; CT = *Chlamydia trachomatis*; MV = main visit; NG = *Neisseria gonorrhoeae*; po = per os; PID = pelvic inflammatory disease; TV = *Trichomonas vaginalis*; UTI = urinary tract infection.

1. May total to more than 100% because one participant could have received multiple treatments.

- 2. The denominator is the number of women who attended at least one AV related to a suspected ongoing untreated infection, re-infection or treatment failure. If one woman attended multiple AVs, the data from these AVs were combined.
- 3. Only includes treatments that were reported at an AV but still relate to symptoms reported at the MV. The reasons why the treatments were not given at the MV will be reported in footnotes. Treatments given at AVs that were based on newly reported symptoms will not be included because these participants should have been referred to a local health centre.

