The following table describes, per possible infection, in what case treatment must be given per protocol. As mentioned before, the Rwandan guidelines include VDS algorithms that do not use risk scoring but use a pelvic examination to distinguish between mucopurulent cervical discharge and/or cervicitis (which is to be treated for CT/NG/TV) and non-muco-purulent vaginal discharge (which is to be treated for BV/TV/Candidiasis). We have decided to not take these algorithms into account.

Treatment given for:	WHO Syndromic Management	Rwandan Syndromic Management	WISH procedures	Gold standard procedures
СТ	Given with VDS and high risk / high local prevalence ¹ ; given with PID (after LAP) ²	Given with VDS and positive risk score ³ ; given with PID (after LAP) ² ; given as presumptive FSW treatment if asymptomatic ⁴	Positive for CT GeneXpert test performed after risk-scoring ⁵	Positive CT GeneXpert test (test performed on everyone)
NG	Given with VDS and high risk / high local prevalence ¹ ; given with PID (after LAP) ²	Given with VDS and positive risk score ³ ; given with PID (after LAP) ² ; given as presumptive FSW treatment if asymptomatic ⁴	Positive for NG after GeneXpert test performed after risk-scoring ⁵	Positive NG GeneXpert test (test performed on everyone)
TV	Given with VDS; covered with PID (after LAP) ²	Given with VDS no matter the risk score ³ ; covered with PID (after LAP) ² ; given as presumptive FSW treatment if asymptomatic ⁴	TV OSOM test	Positive qPCR test for Trichomonas vaginalis
UTI	NA	Treated based on reported symptoms	Positive urine dipstick test after reported symptoms ⁶	ND
BV	Given with VDS; covered with PID (after LAP) ²	Given with VDS and negative risk score ³ ; covered under VDS with positive risk score and PID (after LAP) ²	EcoCare pH swab (all pH ≥ 5.0 results treated)	Positive vaginal health qPCR DNA tool for BV ⁷

 ⁽As calculated by Log₁₀(*Lactobacillus* genus) – Log₁₀(*G. vaginalis* + *A. vaginae*). This DNA tool has a sensitivity and specificity comparable to the Nugent score. Further explained in the article by Jespers V, Crucitti T, [name] J et al. "A DNA tool for early detection of vaginal dysbiosis in African women." Res Microb 167.2 (2016): 133-41.

	on examination ⁸	or without notion of	algorithm after	
		recurrence) on	risk-scoring ⁹	
		examination		
Candidiasis	Given with VDS	Given with VDS and	Given with typical	Positive qPCR
	and typical signs	negative risk score ³	signs and	test for Candida

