- 7. If the participant reports vaginal discharge and (one of) her partner(s) has urethritis or she is positive for a risk score (2 or more positive of: age < 21; being single; 2 or more sexual partners in the past 12 months; new sexual partner in the last 3 months), the participant is to be treated for CT/NG/TV. If the participant reports vaginal discharge, none of her partners have urethritis, and she has a negative risk score (0 or 1 positive of: age < 21; being single; 2 or more sexual partners; new sexual partner in the last 3 months), the participant reports vaginal discharge, none of her partners have urethritis, and she has a negative risk score (0 or 1 positive of: age < 21; being single; 2 or more sexual partners; new sexual partner in the last 3 months), the participant is to be treated for TV/BV/candidiasis.
- 8. Under the Rwandan guidelines, presumptive treatment for CT/NG/TV is given at the STI-related first visit if the patient is an FSW, but only in the absence of symptoms. If symptomatic, the normal algorithms are followed and the presumptive treatment is not given.
- 9. Participant would have received treatment covering CT/NG if she had VDS (with or without LAP) with a positive risk score as described under (8) and/or PID, or if she was an asymptomatic FSW. Participant would have received treatment covering TV/BV if she had VDS (with or without LAP), regardless of the result of the risk score described under (7), and/or PID, or if she was an asymptomatic FSW.

Outcome /		WHO sy	/ndrom	ic man	agement		R	wanda	n syndi	romic n	nanagem	ent		WISH procedures				Gold standard		
treated for	TP1	FP ¹	FN ¹	TN ¹	Sens. ¹	Spec. ¹	TP1	FP ¹	FN ¹	TN ¹	Sens. ¹	Spec. ¹	TP1	FP ¹	FN ¹	TN ¹	Sens. ¹	Spec. ¹	Negative	Positive
N = 705	Ν	Ν	Ν	Ν	%	%	Ν	Ν	Ν	Ν	%	%	Ν	Ν	Ν	Ν	%	%	Ν	Ν
CT ²																				
NG ²																				
CT and/or NG ²																				
TV ³																				
BV ³																				
BV and/or TV ³																				
Candidiasis ⁴																				
Syphilis⁵																				
UTI ⁶																				

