5.4 Overview syndromic management and WISH procedures vs. gold standard testing

An overview table will be made to compare WHO and Rwandan syndromic management, and the procedures of the WISH study, with gold standard testing.

Abbreviations: BV = bacterial vaginosis; CT = Chlamydia trachomatis; FN = false negative; FP = false positive; FSW = female sex worker; GUD = genital ulcer disease; LAP = lower abdominal pain; NA = not applicable; NG = Neisseria gonorrhoeae; PID = pelvic inflammatory disease; POCT = point of care test; Sens. = sensitivity; Spec. = specificity; TN = true negative; TP = true-positive; TV = Trichomonas vaginalis; UTI = urinary tract infection; VDS = vaginal discharge syndrome.

1. Compared to gold standard testing (CT, NG, TV, BV, candidiasis) or WISH procedures reference test (Syphilis, UTI). Sensitivity calculated by TP / (TP + FN); specificity calculated by TN / (TN + FP).

2. Under WHO syndromic management, the participant is treated for CT/NG if she is positive for VDS (with or without LAP) and/or PID. Under Rwandan syndromic management, the participant is treated for CT/NG if she is positive for VDS and (one of) her partner(s) has urethritis or she is positive for a risk score (2 or more positive of: age < 21; being single; 2 or more sexual partners in the past 12 months; new sexual partner in the last 3 months), if she has PID, or if she is an asymptomatic FSW. Under WISH procedures, the participant is offered GeneXpert CT/NG POCT testing if she is positive for the WISH CT/NG risk score previously described, and treated based on the test results. Gold standard is defined as GeneXpert CT/NG POCT performed on everyone.

3. Under WHO syndromic management, the participant is treated for BV/TV if she is positive for VDS (with or without LAP) and/or PID. Under Rwandan syndromic management, the participant is treated for BV/TV is she is positive for VDS (no matter the Rwandan CT/NG risk score described under (2)), if she has PID, or if she is an asymptomatic FSW. Under WISH procedures, the participant is offered TV OSOM POCT testing and treated based on the test results, and is offered BV by pH testing and treated based on the test results (a pH of 5.0 or higher is treated, regardless of symptoms). Gold standard testing is defined as TV qPCR, and BV qPCR vaginal health score, as explained in section 5.1

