2. May be lower than total number of false-positives due to same treatment given for other infections.

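### SAP Table 5.4 counts a woman as treated for BV or TV by different rules in different columns, chiefly in the Rwandan BV cell and in the credit given for PID

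*SAP*

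**What the plan says.** The rows of the overview table in SAP 5.4 are headed as outcome or treated for. Each column gives true and false positives and negatives against the gold standard. The TV, BV, and BV and/or TV rows share footnote 3, which defines treatment as follows.

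- **WHO:** any VDS, and/or PID.
- **Rwandan:** any VDS, "no matter the Rwandan CT/NG risk score described under (2)), if she has PID, or if she is an asymptomatic FSW".
- **WISH, TV:** "Under WISH procedures, the participant is offered TV OSOM POCT testing and treated based on the test results".
- **WISH, BV:** the participant "is offered BV by pH testing and treated based on the test results (a pH of 5.0 or higher is treated, regardless of symptoms".

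Other sections show what the Rwandan branches are for. Footnote 7 of the table in SAP 5.3 assigns VDS with a positive risk score to CT/NG/TV treatment. Footnote 8 says of sex workers without symptoms that "presumptive treatment for CT/NG/TV is given at the STI-related first visit if the patient is an FSW". The per-infection treatment table just before SAP 5.2 describes BV as "covered under VDS with positive risk score and PID (after LAP", and its Rwandan BV cell does not list the sex-worker branch at all.

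On the WISH side, Protocol Appendix 14.3 gives metronidazole as first choice for TV ("Metronidazole 2 g single oral dose" is the first option listed) and for BV, and includes metronidazole in the first-choice PID regimen. SAP 4.1 records a single category, "Metronidazole 7 days po for BV and/or TV". SAP 5.5 acknowledges the overlap in a footnote to its over- and under-treatment counts: "May be lower than total number of false-positives due to same treatment given for other infections". Nothing carries that into 5.4.

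**The concern.** Two rules are in play. Under *named indication*, a woman counts as treated for an infection only if the algorithm treats her for that infection. Under *drug cover*, she counts if the drug she received would also treat it. Footnote 3 uses drug cover for part of the Rwandan BV cell and for PID in both syndromic columns. It uses named indication for WISH.

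So a Rwandan-column woman with BV, given a CT/NG/TV regimen, is a true positive for BV. A WISH woman with BV, pH below 5.0 and a positive OSOM test also receives metronidazole, but is a false negative for BV. A WISH woman given metronidazole for PID earns no TV or BV credit, while the same diagnosis earns it in the other two columns.

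Table 5.4 is the SAP's summary comparison of the three strategies. Part of any difference in its BV row, and of any PID-driven difference in its TV and combined rows, would come from scoring and not from the strategies.

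**Working it through.** Table 5.4 is an empty shell and no sample-size calculation was made, so there is no planned figure to reproduce. The check has two parts.

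**1. Which rule each cell uses**

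| Branch | TV row | BV row |
|---|---|---|
| WHO VDS | named | named |
| Rwandan VDS, negative score | named | named |
| Rwandan VDS, positive score | named | drug cover |
| Rwandan asymptomatic FSW | named | drug cover |
| PID, WHO and Rwandan | drug cover | drug cover |
| WISH OSOM-positive | named | not counted |
| WISH pH 5.0 or higher | not counted | named |
| WISH PID | not counted | not counted |

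In the TV row the only borrowed credit is PID. In the BV row it is PID plus two Rwandan branches.

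**2. What drug cover would do to the WISH cells**

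Inputs: OSOM 77% sensitive and 99% specific, pH 5.0 or higher 71% sensitive and 76% specific (Protocol 3.1); 75 TV and 175 BV cases expected in 500 women, i.e. 15% and 35% (Protocol 4.3); N = 705 (SAP section 2). The Protocol 3.1 table gives TV 10–17% and BV 36–44%, so TV 10–17% and BV 35–44% are used as ranges. The documents give no joint distribution of TV, BV and pH; independence is an assumption.

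*BV row, scored as pH 5.0 or higher or OSOM-positive*

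- OSOM-positive share = 0.15 × 0.77 + 0.85 × 0.01 = 0.124
- Sensitivity = 1 − (1 − 0.71) × (1 − 0.124) = 0.746, against 0.71
- Specificity = 0.76 × (1 − 0.124) = 0.666, against 0.76
- In 705 women (about 247 with BV, 458 without): true positives about 175 → 184, false positives about 110 → 153
- For TV 10% to 17%: sensitivity 73.5% to 75.0%, specificity 69.5% to 65.4%

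*TV row, scored as OSOM-positive or pH 5.0 or higher*

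- Share with pH 5.0 or higher = 0.35 × 0.71 + 0.65 × 0.24 = 0.4045
- Sensitivity = 1 − (1 − 0.77) × (1 − 0.4045) = 0.863, against 0.77
- Specificity = 0.99 × (1 − 0.4045) = 0.590, against 0.99
- With BV 44% the share is 0.4468 and specificity 0.99 × 0.5532 = 0.548. Independence therefore gives 55–59%.
- If every TV-positive woman had pH 5.0 or higher, the share among TV-negative women would be (0.4045 − 0.15)/0.85 = 0.299 and specificity 0.99 × 0.701 = 0.694. Over the prevalence ranges this limit gives 61–71%.

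The direction needs no assumption. Adding treated women to a column cannot lower its sensitivity or raise its specificity. Likewise, dropping the two borrowed branches cannot raise Rwandan BV sensitivity or lower its specificity. The size of that Rwandan change cannot be computed, because the documents do not give the number of women in those branches.

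The combined BV and/or TV row is unaffected by the TV/BV overlap, since either positive test already counts. Only WISH PID treatment is missing from it.

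**The case against.** A reader might infer more: that WISH TV specificity is overstated by some 40 points (99% against 59%) and that WISH over-treatment with metronidazole disappears from view. The documents do not support this, for four reasons.

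- Every WHO and Rwandan VDS or sex-worker branch names TV. Apart from PID, the TV row already follows named indication in all three columns, and under that rule 77%/99% is right. The 59% belongs to a different estimand and also rests on independence of pH and TV.
- The secondary endpoint in SAP 1.1 is framed as accuracy of POC testing against the gold standard, and SAP 5.3 compares TV by POCT with TV by qPCR directly. Footnote 3 states the WISH rule openly.
- Metronidazole given for a falsely high pH counts as a false positive in the BV row, and in the combined row when TV is also absent. It is tabulated by regimen in SAP 5.5 and appears in the treatment counts of SAP 4.1. On the protocol's figures, 0.2485/0.4045 = 61% of women with pH 5.0 or higher would truly have BV, so most of the added TV false positives would be women correctly treated for BV.
- The drug overlap is incomplete: clindamycin is listed for BV only. TV also calls for partner treatment and BV does not, so a BV course is not the same as being managed for TV.

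All of this stands for the TV row. It does not answer the BV row, where the Rwandan cell is credited for regimens aimed at other infections and WISH is not. Nor does it answer the unequal PID credit. The row heading, treated for, makes the mixture hard for a reader to see.

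**Conclusion.** The concern holds in a limited form. Footnote 3 applies different rules across columns, mainly in the Rwandan BV cell and in the PID credit. On the Rwandan drug-cover rule, WISH BV would move from about 71%/76% to about 75%/67%, given TV 15% and an OSOM result independent of BV and pH. WISH TV would move to about 86%/59% under independence, with specificity 55–71% from independence up to the limit in which all TV-positive women have pH 5.0 or higher. The TV figures show how much the choice of rule matters; they are not an error in the planned WISH TV cell. The effects of PID and of the two Rwandan branches have a known direction but no size that the documents can supply. Either rule is defensible, but mixing them in one comparison is not.

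**What to change.** Rewrite footnote 3 so that one rule governs all three columns.

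1. In the single TV and BV rows, score by named indication. Drop VDS with a positive risk score and asymptomatic FSW from the Rwandan BV cell, and bring the treatment table before SAP 5.2 into line, since it omits the FSW branch for BV.
2. Treat PID identically under WHO, Rwandan and WISH management: either it counts in every column or in none.
3. Name the BV and/or TV row as the drug-cover comparison. Score WISH there from the treatments recorded under SAP 4.1, including metronidazole given for PID. The 4.1 category holding PID antibiotics still has its entries to be specified, so it must identify metronidazole.
4. Reconcile the WISH BV rule. Protocol 3.1 also foresees BV treatment at lower pH when symptoms are severe, while SAP 5.4 uses pH alone.

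The cost is a footnote and a re-tabulation of data already collected. Rwandan BV sensitivity and WISH combined-row specificity may look slightly less favourable. Recorded treatments also carry the omissions and errors listed in SAP 5.6, whereas the syndromic columns are reconstructed without such errors. The number of women whose recorded treatment differs from the algorithm should therefore be shown beside the row.

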5.5 Primary and secondary objective outcomes based on gold standard tests

In this section, we will examine the influence of false-negative and false-positive POCT results on the WISH study primary and secondary outcomes. The CT/NG GeneXpert tests of the women scoring negative on the risk score came available relatively quickly after their Main Visit; if their CT/NG GeneXpert test performed later came back positive, participants were called back for treatment and partner notification procedures. This was all done when the WISH study was still active, and will not be reported here. If the TV OSOM test turned out to be false-negative (compared to the gold standard qPCR TV test), participants were urged by cell phone text message to seek diagnosis/treatment elsewhere. The other gold standard tests performed (BV, Candidiasis) do not require partner treatment nor referrals, and thus are not likely to have changed most outcomes except for treatment.

Abbreviations: BV = bacterial vaginosis; TV = Trichomonas vaginalis.

1. May be lower than total number of false-negatives due to same treatment given for other infections.

Results at Main Visit – false-negative and false-positive TV POCT test	N = 705
False-negative TV OSOM result N	
False-positive TV OSOM result N	
Number of partners that should have been notified based on window period and false-	
negative results N	
Over-treatment given due to false-positive TV OSOM result ¹ n (%):	
- Metronidazole single dose	
- Metronidazole 7 days	
- other, [categories to be made]	
Number of women that should have been treated for false-negative TV OSOM result ² N	
Results at Main Visit – false-negative and false-positive BV POCT test	N = 705
False-negative BV by pH testing results N	
False-positive BV by pH testing results N	
Over-treatment given due to false-positive BV result ¹ n (%):	
- Metronidazole single dose	
- Metronidazole 7 days	
- other, [categories to be made]	
Number of women that should have been treated for false-negative BV result ² N	
Results at Main Visit – false-negative and false-positive candidiasis diagnosis	N = 705
False-negative Candidiasis diagnoses N	
False-positive Candidiasis diagnoses N	
Over-treatment given due to false-positive Candidiasis diagnosis n (%):	
- Fluconazole single dose for vaginal candidiasis	
- Clotrimazole pessaries 3 nights for vaginal candidiasis.	
Number of women that should have been treated for false-negative Candidiasis result N	

2. May be lower than total number of false-positives due to same treatment given for other infections.

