Bacterial vaginosis Vaginal pH is 5.0 or higher. Treat regardless of the presence of symptoms.	
 
1st choice: Metronidazole 400 or 500 mg orally twice per day for 7 days OR Metronidazole 2g single oral dose.
 
2nd choice: Tinidazole 2g orally once a day for 2 days or 1g per day for 5 days.
 
Alternative: Clindamycin 300 mg orally twice per day for 7 days
 
	
 
Metronidazole 2g single oral dose is a less effective treatment for BV than the 7-day treatment. Only give a single oral dose if you are worried that the patient will not be adherent for 7 days.
 
Women should be encouraged to wear clean underwear daily, not wash inside the vagina (and if this cannot be avoided, to use clean plain water only), and use hormonal contraception to prevent recurrence.
 
Male partners are not treated but women should be told that BV-associated bacteria can be passed between sexual partners. Their male partners should be encouraged to improve their penile hygiene and clean underneath the foreskin regularly.
 

Vaginal candidiasis When symptoms typical for vaginal candidiasis are present: White, curd-like, odorless vaginal discharge with vaginal itching and/or burning.	
 
1st choice: Fluconazole 150 mg single oral dose
 
2nd choice: Clotrimazole 200 mg pessaries every night for 3 nights
 
	
 
Do not treat without lab confirmation; do not treat if asymptomatic)
 
Male partners are not notified but if a male partner has symptoms of balanoprosthitis, he can be given 1% Clotrimazole cream to be applied for 14 days.
 
Patients should be counseled to abstain from sex or use condoms, until symptoms have cleared.
 

Diagnosis	Treatment Other Follow-Up		

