1.3 WISH study procedures

All participants attended a Main Visit, during which the following procedures were done in the order given: eligibility check, informed consent procedures, assignment of Patient Identification Number (PID), face-to-face interview including CT/NG and syphilis risk scoring, counselling (the participant could choose the topics she wanted to be counselled on herself), and a pelvic and bimanual examination if the participant reported relevant and moderate/severe urogenital symptoms (see paragraph 4.1, section "Pelvic, bimanual and physical examinations performed at Main and Additional Visits", for details).

Participants were offered the following additional services:

- a) Voluntary counselling and testing (VCT) for HIV.
- b) Urine pregnancy test if indicated.
- c) POC testing for UTI if UTI symptoms were present.
- d) POC testing for TV and BV regardless of symptoms, and management of vaginal candidiasis based on symptom-reporting and/or signs during a pelvic examination (if applicable).
- e) POC testing for syphilis and/or CT/NG if considered at risk by risk scoring (such as being pregnant).
- f) Syndromic management of LAP, genital ulcer syndrome (GUD) and inguinal buboes.
- g) Treatment and partner notification and treatment as appropriate, and referrals to antenatal, family planning, HIV and cervical cancer screening care.

Services were available for free at RU's research clinic for the duration of the project. Services were generally delivered within one half day. However, women could choose to leave before all results were available, and be contacted by study staff when results were available, which was particularly relevant for women undergoing CT/NG POC testing (this was performed on the Cepheid GeneXpert platform, which takes about 90 minutes).

Additional Visits took place when participants opted not to wait for test results, for partner notification and treatment, if urogenital symptoms did not resolve after treatment, and for other reasons that are summarised in this SAP. Women could notify partners themselves or allow RU staff to contact partners. They could also opt out of partner notification of specific partners, for example, if there was a risk of domestic violence. Participants who developed new urogenital symptoms were referred to local clinics because each woman was allowed to participate in the WISH study only once.

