Pelvic, bimanual and physical examinations performed at Main and Additional Visits: At the Main Visit, speculum and bimanual examinations were only performed if the participant reported relevant and moderate/severe urogenital symptoms. If she only had UTI-related symptoms (burning when passing urine, frequent urination or urge to urine, or blood in urine), a speculum and bimanual examination was not offered, and UTI testing and treatment were offered based on symptom-reporting. In the case of candidiasis-related symptoms (curdlike unusual vaginal discharge and genital itching), a speculum and bimanual examination was done at the discretion of the study physician; the protocol allowed the study physician to treat the participant based on the reported symptoms alone. If a pelvic and bimanual examination was performed, and no signs of vaginal candidiasis were seen, no treatment for vaginal candidiasis was given.

During Additional Visits, a pelvic and bimanual examinations were only performed if the participant had not had an examination at the Main Visit (for example, because she was menstruating), or if her symptoms had not resolved after having received treatment.

Speculum, bimanual, and physical examinations	MV n (%)	AV n (%)
	N = 705	N = 705
N women who underwent a speculum exam	•	
Reason for speculum exam ⁺ :	N = XXX	N = XXX
- To evaluate symptoms		
- At the participant's request		
- Another reason, specify [additional categories to be made if needed]	••	
Any abnormalities observed by physician during speculum exam	N = xxx	N = xxx
If yes, which one(s) ¹ :	N = xxx	N = xxx
- Enlarged/tender inguinal lymph nodes		
- Abnormal (genital) odour		
- Warts or condylomata (any location genitalia)		
- Ulcers/blisters/sores suggestive of STI in vulva		
- Vulvitis		
- Any other lesion on vulva		
- Vaginal mass (polyp, myoma, etc.)		
- Ulcers/blisters/sores suggestive of STI in vagina		
- Vaginitis		
- Any other lesion on vaginal epithelium		
- Cervicitis		
- Any other lesion on cervical epithelium		
- Abnormal vaginal or cervical discharge/pus		
- Other, specify [additional categories to be made if needed]		
N women who underwent a bimanual exam		
Any abnormalities observed by physician during bimanual exam	N = xxx	N = xxx
If yes, which one(s) ¹ :	N = xxx	N = xxx
- Uterine mass		
- Adnexal mass on the right		
- Adnexal mass on the left		
- Uterine tenderness		
- Adnexal tenderness on the right		
- Adnexal tenderness on the left		
- Cervical motion tenderness		

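### SAP 5.5 counts missed candidiasis treatment with no symptom or sign condition, so it includes qPCR-positive women whom the protocol says not to treat

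*SAP*

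**What the plan says.** SAP 5.5 examines what false POCT results, judged against the gold standard, meant for the study's outcomes. For each of TV, BV and candidiasis it lists false negatives, false positives, over-treatment and missed treatment. The last candidiasis row reads "Number of women that should have been treated for false-negative Candidiasis result N". The TV and BV versions of that row carry a footnote allowing for the same drug having been given for another infection; the candidiasis row carries none. The introduction to 5.5 says that the BV and candidiasis gold-standard results need no partner treatment or referral and "thus are not likely to have changed most outcomes except for treatment".

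SAP 5.3 defines the comparison as being treated for candidiasis against *C. albicans* qPCR. SAP 4.2 says the swabs were collected per participant at the Main Visit.

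The treatment rule is elsewhere. Protocol Appendix 14.3 gives the criterion "When symptoms typical for vaginal candidiasis are present" and instructs "do not treat if asymptomatic". For the other two infections the same appendix says "Positive TV OSOM test. Treat regardless of the presence of symptoms" and "Vaginal pH is 5.0 or higher. Treat regardless of the presence of symptoms". SAP 1.3 ties candidiasis management to reported symptoms, to signs on a pelvic examination, or to both. SAP 4.1 adds that where an examination was done and "no signs of vaginal candidiasis were seen, no treatment for vaginal candidiasis was given".

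**The concern.** The missed-treatment row takes a detection result and turns it into a statement about care. For TV and BV that step is reasonable, because the protocol wants both treated whether or not the woman has symptoms. For candidiasis it is not: a known positive qPCR in a woman with neither typical symptoms nor signs would still have led to no treatment under the protocol.

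Treatment is the one outcome that 5.5 expects the candidiasis results to change, so this row is the main care consequence reported for missed candidiasis. If it is filled in as written, a reader will take the whole false-negative count as under-treatment by WISH procedures, although part of it is the protocol being followed.

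**Working it through.** The table shell is unfilled, so there is no figure of the plan's to reproduce. The check is of definitions, followed by an illustration of size.

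**Step 1: who enters the row.** From SAP 5.3, a false negative is a qPCR-positive woman not treated for candidiasis. I assume that 5.5 uses the same definition. With no further filter and no footnote, the missed-treatment row equals the false-negative count.

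**Step 2: what the protocol would have done with a known positive.**

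| Untreated qPCR-positive woman | Protocol rule | Missed treatment? |
|---|---|---|
| Typical symptoms or signs, no examination ruling it out | Treat (Protocol 3.1, Appendix 14.3, SAP 1.3) | Yes |
| Typical symptoms, examination showed no signs | Untreated under SAP 4.1, but she meets the Appendix 14.3 symptom criterion and the qPCR confirms the organism | Yes |
| Neither typical symptoms nor signs | Do not treat (Appendix 14.3) | No |

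The row as written counts all three groups.

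**Step 3: does the conflict inside Appendix 14.3 matter?** The candidiasis cell also says not to treat without laboratory confirmation. That conflicts with Protocol 3.1, which treats on symptoms alone. Under Protocol 3.1, symptoms are required. With both halves of the cell taken together, symptoms and a laboratory result are required. Neither reading makes a positive result alone a reason to treat, so the third group stays out either way.

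**Step 4: illustration of size.** Let *N* be the women enrolled, *p* the qPCR positivity, and *s* the share of positives who are untreated with neither typical symptoms nor signs. The excess in the row is *N* × *p* × *s*.

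- *N* = 705 (SAP 2).
- *p* = 7% and 10%, from the two high-risk columns of the Protocol 3.1 prevalence table. Protocol 4.3 plans on 50/500 = 10%.
- *s* is not in the documents; 10%, 50% and 80% are assumptions.

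Positives: 705 × 0.07 = 49.35 and 705 × 0.10 = 70.5, so about 49 to 71.

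| Assumed *s* | Excess at *p* = 7% | Excess at *p* = 10% |
|---|---|---|
| 10% | 4.9 | 7.1 |
| 50% | 24.7 | 35.3 |
| 80% | 39.5 | 56.4 |

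To set this beside the row itself, take *p* = 10%, half of positives with neither symptoms nor signs and none of these treated, and 70% of the other half treated (all assumed except *p*). The row as written is 35.25 + 0.30 × 35.25 = 45.8, about 46. With a symptom or sign condition it is 10.6, about 11.

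These figures are weak guides. The Protocol 3.1 table does not say how candidiasis was diagnosed, so qPCR positivity may differ from 7–10%. Protocol 3.1 also says that candidiasis typically becomes symptomatic as the load rises, which favours a lower *s*.

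**The case against.** The strongest reply is that 5.5 is explicitly about outcomes under gold-standard testing. The SAP's table of treatment rules (before 5.2) has a gold-standard column whose candidiasis entry is a positive qPCR. On that view, replacing the WISH diagnostic step with qPCR removes the symptom condition by design. This justifies qPCR as the reference for detection, and the false-negative row should stay. It does not justify the care label: the table is introduced as describing when the protocol requires treatment, and nothing in the protocol makes a positive *Candida* result alone such a reason.

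A second reply is that the contrast with BV is not perfect. Appendix 14.3 triggers BV treatment by pH, and a BV false negative has a pH below 5.0, which Protocol 3.1 treats only for severe symptoms. That is correct as far as it goes. Protocol 3.1 nevertheless argues for treating asymptomatic BV in principle, and makes no such argument for candidiasis.

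A third is that a narrowed row would mostly repeat the lapses already listed in SAP 5.6 as candidiasis diagnoses left untreated. That would be so if symptomatic women with a negative examination were excluded. They should be kept: they were not lapses when seen, and they are the missed cases that gold-standard testing can reveal.

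It also stands that the block judges over-treatment by qPCR, although women in that row may have been treated correctly under the symptom-based rule. A change to one side needs a note on the other.

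**Conclusion.** The point holds, at low severity. As written, the row overstates under-treatment by the number of untreated qPCR-positive women with neither typical symptoms nor signs. That number cannot be computed from the documents; the range of about 5 to 56 women rests on borrowed prevalences and assumed shares.

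A reader might infer three stronger things that the documents do not support:

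- **That the accuracy estimates for candidiasis are wrong.** They are not affected. SAP 5.3 and 5.4 state that the reference is qPCR, and sensitivity, specificity, PPV and NPV follow from that choice.
- **That the whole row is invalid.** Untreated positives with typical symptoms or signs belong in it, including those whose examination showed no signs.
- **That the TV and BV rows share the fault.** The protocol supports treating both without symptoms.

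A separate false-negative row exists, so a narrower missed-treatment count may have been intended, but no narrowing rule is written.

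**What to change.** Leave the false-negative row in 5.5 and the candidiasis rows in 5.3 and 5.4 as they are, with a note that they measure *C. albicans* detection by qPCR regardless of symptoms. Split the missed-treatment row using Main Visit data:

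- (a) Untreated qPCR-positive women with typical candidiasis symptoms or signs, including symptomatic women whose examination showed no signs: counted as missed treatment.
- (b) Untreated qPCR-positive women with neither: labelled *C. albicans detected without typical symptoms or signs; treatment not indicated per protocol*.

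State in a footnote which recorded symptoms and findings count as typical. Add a second footnote that the over-treatment rows are judged against qPCR and that those women may have been treated correctly under the symptom-based rule.

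The cost is one descriptive row split in two and a few notes. The symptoms and examination findings are already collected for SAP 4.1, so no new data or testing is needed.
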